	Day 1 ^b	Day 3 (± 1 day)	Day 15 (± 3 days) and Week 4 (± 1 week)	Week 8, Week 16, Week 24, Week 36, Week 48 (± 1 week)	Week 12, Week 20 (± 1 week)	Week 60, Week 84 (± 1 week)	Week 72 (± 1 week)		
Meal(s) or snack(s) at site ⁱⁱ	X		X	X		X	X	X	
Study drug dosing ^{gg,ff}		LUM 200 mg q12h/IVA 250 mg q12h OR LUM 400 mg q12h/IVA 250 mg q12h ^{hh}							
Observation 4 hours after the first dose	X								
Study drug count			X	X		X	X	X	
Concomitant medications		Continuous, from signing of ICF (and assent form, if applicable) through Safety Follow-up Visit							
Concomitant treatments and procedures		Continuous, from signing of ICF (and assent form, if applicable) through Safety Follow-up Visit							
AEs and SAEs ⁱⁱ		Continuous, from signing of ICF (and assent form, if applicable) through Safety Follow-up Visit							

AE: adverse event; ALP: alkaline phosphatase; ALT: alanine aminotransferase; AST: aspartate aminotransferase; β-hCG: beta-human chorionic gonadotropin; BMI: body mass index; CF: cystic fibrosis; CFQ-R: CF Questionnaire-Revised; [REDACTED]-ECG: electrocardiogram; GGT: gamma glutamyl transpeptidase; ICF: informed consent form; IEC: independent ethics committee; IRB: institutional review board; [REDACTED] IVA: ivacaftor; LCI: lung clearance index; LFT: liver function test; LUM: lumacaftor; [REDACTED] q12h: every 12 hours; SAE: serious adverse event; TSQM: Treatment Satisfaction Questionnaire for Medication.

Fat-containing food such as a standard CF high-fat, high-calorie meal or snack (Section 10.2) will be provided at the site to subjects after all pre-dose assessments have occurred.

^{gg} The study drug should be administered every 12 hours (± 2 hours) within 30 minutes of consuming fat-containing food (Section 10.2). On days of scheduled visits, the dose of study drug will be administered at the site after pre-dose assessments have been completed. The last dose of study drug will be administered at the Week 96 Visit.

^{hh} Subjects who turn 12 years of age in the previous study or Day 1 of this rollover study will begin receiving LUM 400 mg q12h/IVA 250 mg q12h on Day 1. Subjects who turn 12 years of age after the Day 1 Visit of this rollover study will begin receiving LUM 400 mg q12h/IVA 250 mg q12h at their next scheduled visit.

ⁱⁱ SAEs that occur after the Safety Follow-up Visit and are considered related to study drug(s) will be reported to Vertex GPS within 24 hours as described in Section 13.1.2.2.

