Ongoing Studies 011 Part B and 109 are designed to obtain PK, safety, tolerability, PD, and efficacy (Study 109 only) information to support an expanded indication for lumacaftor and ivacaftor combination therapy in the pediatric population (subjects 6 through 11 years of age, inclusive, who are homozygous for the *F508del-CFTR* mutation). Study 109 is designed to compare active treatment (LUM 200 mg q12h/IVA 250 mg q12h) with a matched placebo treatment for 24 weeks.

The long-term safety of lumacaftor in combination with ivacaftor has not yet been evaluated in subjects aged 6 through 11 years. Therefore, the primary objective of this study is to evaluate the long-term safety and tolerability of lumacaftor in combination with ivacaftor in subjects aged 6 years and older with CF, homozygous for the *F508del-CFTR* mutation, and who rollover from Study 109 or Study 011 Part B.

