Weight, Height, and BMI: Malnutrition is common in patients with CF because of increased energy expenditures due to lung disease and fat malabsorption. Given that lumacaftor in combination with ivacaftor is a systemic therapy, it has the potential to improve extrapulmonary manifestations of CF, including those in the gastrointestinal system. Improved nutritional status, defined as an increase in weight and/or BMI, is considered an appropriate endpoint for therapies targeting exocrine pancreatic manifestation of CF and was explored in previous clinical studies of CFTR-targeted therapies (Studies VX08-770-102 and VX08-770-103 and Studies 103 and 104).

As children gain weight and height as part of normal growth, adjustment for age and sex is necessary to assess changes in nutritional status in a population of boys and girls in varying stages of growth. To evaluate the effect of lumacaftor in combination with ivacaftor on growth and nutrition adjusted for age and sex, weight-for-age, height-for-age, BMI-for-age,

and the respective z-scores will be determined. Height and weight will be collected at the study visits indicated in the schedule of assessments.

Sweat Chloride: In patients with CF, the underlying CFTR ion transport defect results in elevated sweat electrolyte levels.^{34,35} The sweat chloride test (quantitative pilocarpine iontophoresis) is the most common diagnostic tool for CF. A sweat chloride concentration of ≥ 60 mmol/L is considered to be diagnostic of CF, whereas < 40 mmol/L is considered normal. Based on the mechanism of action of lumacaftor and ivacaftor, the sweat chloride test was included in this study as a measure of the PD effect on CFTR activity when lumacaftor is administered in combination with ivacaftor.

CFQ-R: The CFQ-R is a validated CF-specific instrument that measures the health-related quality of life of patients with CF.^{36,37,38} The CFQ-R measures quality-of-life domains including respiratory symptoms, digestive symptoms, emotion, and health perception. Furthermore, the CFQ-R has been evaluated in clinical studies involving therapies for CF lung disease.^{39,40,41} Linguistically-validated versions of the CFQ-R^{42,43} are available, thereby allowing consistent interpretation of the results in global studies.

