12.1 Sample Size and Power

This is a rollover study that plans to enroll subjects from qualifying previous studies (Study 109 and Study 011B) who meet the inclusion and exclusion criteria for this study. Approximately 256 subjects are potentially eligible to be enrolled into Study 110: approximately 200 subjects from Study 109 and approximately 56 subjects from Study 011B, if eligible. Table 12-1 provides the 95% CIs assuming different incidence of CF lung (preferred term for pulmonary exacerbation) in CF subjects.

Table 12-1 95% Confidence Intervals Assuming Different Observed Incidences of CF lung (n = 256)

Observed CF lung incidence	95% Confidence Interval
0.1	(0.063, 0.137)
0.2	(0.151, 0.249)
0.3	(0.244, 0.356)
0.4	(0.340, 0.460)

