12.4.3 Efficacy Analysis

Assessment of the efficacy and durability of long-term treatment with lumacaftor in combination with ivacaftor in the Treatment Cohort is a secondary objective of this study.

For continuous efficacy variables: Lung clearance index ($LCI_{2.5}$ and $LCI_{5.0}$) (for subjects rolled over from Study 109 and the Study 011B LCI Substudy), sweat chloride, $ppFEV_1$ (both absolute change and relative change), BMI and BMI-for-age z-score, weight and weight-for-age z-score, height and height-for-age z-score, CFQ-R respiratory domain, and

TSQM, raw values and absolute change (or relative change) from baseline, at each visit, will be summarized. Descriptive statistics including number of subjects (n), mean, SD, standard error (SE), median, minimum, and maximum will be provided. In addition, 95% CI of the mean will be presented.

For the analyses of LCI and ppFEV₁, a mixed-effect repeated-measure model (MMRM) will be fitted for the cumulative dosing period, including visits from the previous Study 109 and Study 011B and visits from the current Study 110 based on IFAS. In the MMRM models for the cumulative dosing period, the absolute change from baseline of the previous study (including all predose measurements at each visit in the cumulative dosing period, both on-treatment measurements and measurements after treatment discontinuation), will be included as the dependent variable; treatment group, visit, and treatment-by-visit interaction as fixed effects; and subject as a random effect with adjustment for previous study (Study 109 versus Study 011B), weight (<25 kg versus ≥25 kg), and ppFEV₁ severity (<90 versus ≥90), both as determined at screening in the previous study. In the analysis of LCI, baseline LCI value will also be included as a continuous covariate in the MMRM model. The result obtained from the model will be the treatment effect at each postbaseline visit. The estimated mean treatment effect, a 95% CI, and a 2-sided *P* value will be provided. The least squares (LS) means (95% CI) at each visit will be plotted by treatment group.

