10.4.2 Clinical Laboratory

Treatment Cohort Period 1

For the laboratory measurements, the raw values and change from previous study baseline of the continuous hematology and chemistry results will be summarized in System International (SI) units at each scheduled time point in the Cumulative Study Period based on the Safety Set.

The number and percentage of subjects meeting the defined threshold criteria during the treatment-emergent period will be summarized. The threshold criteria are provided in Appendix H. For LFT results (alanine aminotransferase [ALT], aspartate aminotransferase [AST], serum alkaline phosphatase [ALP], and total bilirubin), the following analyses will be conducted:

- The mean values (95% CI) will be plotted against visit for all the visits in the Cumulative Study Period for ALT and AST.

- A listing for subjects with elevated LFT results during the treatment-emergent period of the Cumulative Study Period will be presented. The listing will include all parameters of the LFT assessment at all visits.

The number and percentage of subjects with shift changes from baseline in ALT, AST, ALP and total bilirubin (normal/missing, high, low, according to the reference range), based on the worst on-treatment laboratory evaluation, will be tabulated.

Results of urinalysis and the serum pregnancy test will be listed in individual subject data listings only. A listing containing individual subject hematology, chemistry, and coagulation values will be provided with a column indicating outside reference range or not. This listing will include data from scheduled and unscheduled time points.

Treatment Cohort Period 2

For Treatment Cohort Period 2 LFT results (ALT, AST, ALP, and total bilirubin), the following analyses will be conducted:

- The number and percentage of subjects meeting the defined threshold criteria during the treatment-emergent period of Treatment Cohort Period 2 will be summarized. The threshold criteria are provided in Appendix H.
- A listing for subjects with all LFT results during the treatment-emergent period of the Treatment Cohort Period 2 will be presented. The listing will include all parameters of the LFT assessment at all visits.

Results of urine pregnancy test will be listed in individual subject data listing.

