Appendix H Criteria for Threshold Analysis

Table 13-9 Threshold Analysis Criteria for Laboratory Tests

Parameter	Threshold Analysis	Comments
Clinical Chemistry		
ALT	$\leq 3xULN$ $>3x - \leq 5xULN$ $>5x - \leq 8xULN$ $>3xULN$ $>5xULN$ $>8xULN$	FDA DILI Guidance Jul 2009.
AST	$\leq 3xULN$ $>3x - \leq 5xULN$ $>5x - \leq 8xULN$ $>3xULN$ $>5xULN$ $>8xULN$	FDA DILI Guidance Jul 2009.
ALT or AST	ALT>3xULN or AST>3xULN	Vertex LFT working group 2014
Alkaline Phosphatase	>1.5xULN	FDA DILI Guidance Jul 2009.
Total Bilirubin	$>1.5x - \leq 2xULN$ $>2xULN$	FDA DILI Guidance Jul 2009.
ALT and Total Bilirubin	ALT>3xULN and TBILI>2xULN	FDA DILI Guidance Jul 2009. To be counted within a same treatment phase, whatever the interval between measurement.
AST and Total Bilirubin	AST>3xULN and TBILI>2xULN	FDA DILI Guidance Jul 2009. To be counted within a same treatment phase, whatever the interval between measurement.
(ALT or AST) and Total Bilirubin	(ALT>3xULN or AST>3xULN) and TBILI>2xULN	Vertex LFT working group 2014
CPK	$>3x - \leq 10xULN$ $>10xULN$	FDA Feb 2005. Am J Cardiol April 2006.
Creatinine	$\geq 150 \mu\text{mol/L}$ (Adults) $\geq 30\%$ change from baseline $\geq 100\%$ change from baseline	Benichou C., 1994.
Creatinine Clearance (Cockcroft's formula)	<30 ml/min (severe renal impairment) $\geq 30 - <50$ ml/min (moderate renal impairment) $\geq 50 - \leq 80$ ml/min (mild renal impairment)	FDA criteria May 1998.
Uric Acid		Harrison- Principles of internal Medicine 17 th Ed., 2008.
Hypouricemia	<120 $\mu\text{mol/L}$	
Hyperuricemia	>408 $\mu\text{mol/L}$	
Blood Urea Nitrogen	≥ 17 mmol/L	
Chloride	<85 mmol/L >115 mmol/L	
Sodium	≤ 129 mmol/L ≥ 150 mmol/L	

Table 13-9 Threshold Analysis Criteria for Laboratory Tests

Parameter	Threshold Analysis	Comments
Potassium	<3 mmol/L ≥5.5 mmol/L	FDA Feb 2005.
Total Cholesterol	≥7.74 mmol/L	Threshold for therapeutic intervention.
Triglycerides	≥4.6 mmol/L	Threshold for therapeutic intervention.
Glucose		
Hypoglycaemia	≤3.9 mmol/L and <LLN	ADA May 2005.
Hyperglycaemia	≥11.1 mmol/L (unfasted); ≥7 mmol/L (fasted)	ADA Jan 2008.
HbA1c	>8%	
Albumin	≤25 g/L	
CRP	>2xULN or >10 mg/L (if ULN not provided)	FDA Sept 2005.
Hematology		
WBC	<3.0 Giga/L (Non-Black); <2.0 Giga/L (Black) ≥16.0 Giga/L	Increase in WBC: not relevant. To be interpreted only if no differential count available.
Lymphocytes	>4.0 Giga/L	

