Neutrophils	<1.5 Giga/L (Non-Black); <1.0 Giga/L (Black)	International Consensus meeting on drug-induced blood cytopenias, 1991. FDA criteria.
Monocytes	>0.7 Giga/L	
Basophils	>0.1 Giga/L	
Eosinophils	>0.5 Giga/L or >ULN (if ULN ≥0.5 Giga/L)	Harrison- Principles of internal Medicine 17 th Ed., 2008.
Hemoglobin	≤115 g/L (Male); ≤95 g/L (Female) ≥185 g/L (Male); ≥165 g/L (Female) Decrease from Baseline ≥20 g/L	Criteria based upon decrease from baseline are more relevant than based on absolute value. Other categories for decrease from baseline can be used (≥30 g/L, ≥40 g/L, ≥50 g/L).
Hematocrit	≤0.37 v/v (Male) ; ≤0.32 v/v (Female) ≥0.55 v/v (Male) ; ≥0.5 v/v (Female)	
RBC	≥6 Tera/L	
Platelets	<100 Giga/L ≥700 Giga/L	International Consensus meeting on drug-induced blood cytopenias, 1991.

Table 13-10 Threshold Analysis Criteria for ECGs

CRITERIA for THRESHOLD ANALYSIS of ECGs		
Ref.: CPMP 1997 guideline.		
Parameter	Threshold Analysis	Comments
HR	≤ 50 bpm and decrease from baseline ≥ 20 bpm ≥ 120 bpm and increase from baseline ≥ 20 bpm	
PR	≥ 220 ms and increase from baseline ≥ 20 ms	
QRS	≥ 120 ms	
QTc	Absolute values (ms)	To be applied to any kind of QT correction formula.
Borderline	Borderline: 431-450 ms (Male); 451-470 ms (Female)	
Prolonged*	Prolonged: >450 ms (Male); >470 ms (Female)	
Additional	≥ 500 ms	
	Increase from baseline	
	Borderline: Increase from baseline 30-60 ms	
	Prolonged: Increase from baseline >60 ms	

Table 13-11 Threshold Analysis Criteria for Vital Signs

CRITERIA for THRESHOLD ANALYSIS of VITAL SIGNS		
Parameter	Threshold Analysis	Comments
HR	≤ 50 bpm and decrease from baseline ≥ 20 bpm ≥ 120 bpm and increase from baseline ≥ 20 bpm	To be applied for all positions (including missing) except STANDING.
SBP	≤ 95 mmHg and decrease from baseline ≥ 20 mmHg ≥ 160 mmHg and increase from baseline ≥ 20 mmHg	To be applied for all positions (including missing) except STANDING.
DBP	≤ 45 mmHg and decrease from baseline ≥ 10 mmHg ≥ 110 mmHg and increase from baseline ≥ 10 mmHg	To be applied for all positions (including missing) except STANDING.
Orthostatic Hypotension		
Orthostatic SBP	≤ -20 mmHg	
Orthostatic DBP	≤ -10 mmHg	
Weight	$\geq 5\%$ increase from baseline $\geq 5\%$ decrease from baseline	FDA Feb 2007.

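### The unadjusted 5% weight-gain criterion in the SAP's safety tables will mostly count normal growth over 96 to 120 weeks; the Cockcroft clearance row has a smaller, conditional form of the same fault

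*SAP*

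**What the plan says.** The population comes from studies of "subjects 6 through 11 years of age, inclusive, who are homozygous" for the mutation (Protocol 8.2.1). Treatment in Study 110 runs to week 96: "The last dose of study drug will be administered at the Week 96 Visit". With 24 weeks in the parent study, cumulative follow-up is about 120 weeks. The models stratify on "weight (<25 kg versus ≥25 kg", so children under 25 kg are expected.

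SAP Appendix H sets the safety thresholds. Table 13-11, titled "CRITERIA for THRESHOLD ANALYSIS of VITAL SIGNS", has a weight row with two criteria, a gain and a loss of at least 5% from baseline. Neither is scaled for age or sex. SAP 10.4.4 counts subjects who meet one or more of the vital-sign criteria, in the column layout of SAP 10.1.2.

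Table 13-9 has a row "Creatinine Clearance (Cockcroft's formula" with bands below 30, 30 to below 50, and 50 to 80 ml/min, labelled severe, moderate and mild renal impairment. The row carries no age or body-size limit, although the absolute creatinine limit just above it is marked as applying to adults. SAP 10.4.2 applies the laboratory criteria generally: "The number and percentage of subjects meeting the defined threshold criteria during the treatment-emergent period will be summarized".

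Protocol 8.2.3 explains why z-scores are derived: "As children gain weight and height as part of normal growth, adjustment for age and sex is necessary" to assess nutritional change in growing boys and girls.

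**The concern.** A fixed percentage gain is a usable alert in adults, whose weight should be roughly stable. In children followed for two years it is a measure of time. If nearly every long-observed child passes it, the row says nothing about the drug, and a combined count that includes it says little about heart rate or blood pressure.

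The column layout adds a second problem. Placebo is observed for 24 weeks, while L/I Overall pools about 120 weeks (L200/I-L/I) with 96 weeks (P-L/I). SAP 10.1.2.1 provides exposure-adjusted counts for AE-related data only, so this row appears as a crude n (%). Normal growth would then look like an excess on active drug, within the analyses that serve the primary objective.

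The clearance row raises a similar question. A formula proportional to body weight, graded in absolute ml/min and with no change from baseline required, can flag a child for being small.

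**Working it through.** **The plan's own figure.** The documents give no expected share of subjects meeting a threshold. The only planning figure is the set of confidence intervals at n = 256 (Protocol Table 12-1; "Approximately 256 subjects are potentially eligible to be enrolled into Study 110"). With p ± 1.96·√(p(1−p)/256), incidences of 0.1, 0.2, 0.3 and 0.4 give (0.063, 0.137), (0.151, 0.249), (0.244, 0.356) and (0.340, 0.460). All four rows reproduce, and none depends on this point.

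**Step 1: growth rate that just reaches +5%.** The formula is 1.05^(52/weeks) − 1.

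- 24 weeks: 1.05^(52/24) − 1 = 11.15% a year
- 96 weeks: 1.05^(52/96) − 1 = 2.68% a year, or 0.05 × 25 × 52/96 = 0.68 kg a year at 25 kg
- 120 weeks: 1.05^(52/120) − 1 = 2.14% a year, or 0.05 × 25 × 52/120 = 0.54 kg a year at 25 kg

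**Step 2: weeks to +5% at growth rate g.** The formula is 52·ln(1.05)/ln(1+g). The growth rates are illustrative; the documents give none.

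| Growth per year | Weeks to +5% | Gain at 24 wk | Gain at 96 wk | Gain at 120 wk |
|---|---|---|---|---|
| 2% | 128 | 0.9% | 3.7% | 4.7% |
| 3% | 86 | 1.4% | 5.6% | 7.1% |
| 5% | 52 | 2.3% | 9.4% | 11.9% |
| 8% | 33 | 3.6% | 15.3% | 19.4% |
| 10% | 27 | 4.5% | 19.2% | 24.6% |
| 12% | 22 | 5.4% | 23.3% | 29.9% |

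A child growing at 3% to 11% a year is therefore not flagged in a 24-week column but is flagged in a 96-week one.

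**Step 3: share of subjects flagged.** Assume each child's annual gain is normally distributed with mean 5% to 10% and SD 3% to 4%.

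- By week 96: z = (2.68 − 5)/3 = −0.77 gives 78% (200 of 256); z = (2.68 − 10)/4 = −1.83 gives 97% (247 of 256).
- By week 120: 83% to 97.5% (212 to 250 of 256).
- By week 24: z = (11.15 − 5)/3 = 2.05 gives 2%; z = (11.15 − 10)/4 = 0.29 gives 39%.

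The contrast between a 24-week and a 96-week column arises here with no drug effect at all.

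**Step 4: clearance row.** The SAP names the formula without printing it. The usual form is assumed: (140 − age) × kg / (72 × creatinine in mg/dL), times 0.85 for girls. The creatinine values and the age-weight pairs are also assumptions. Cells show boy / girl in ml/min.

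| Age, weight | 0.3 | 0.4 | 0.5 | 0.6 |
|---|---|---|---|---|
| 6 y, 18 kg | 112 / 95 | 84 / 71 | 67 / 57 | 56 / 47 |
| 6 y, 20 kg | 124 / 105 | 93 / 79 | 74 / 63 | 62 / 53 |
| 8 y, 25 kg | 153 / 130 | 115 / 97 | 92 / 78 | 76 / 65 |
| 9 y, 28 kg | 170 / 144 | 127 / 108 | 102 / 87 | 85 / 72 |
| 10 y, 32 kg | 193 / 164 | 144 / 123 | 116 / 98 | 96 / 82 |

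At 0.3 mg/dL nobody falls to 80 or below. At 0.4 only the 18 and 20 kg girls do. At 0.6 the mild band reaches boys up to 25 kg and a 28 kg girl, and the 18 kg girl falls into the moderate band. At 40 kg and above nobody is flagged even at 0.7 (12 y, 40 kg: 102 / 86).

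**The case against.** The defence has several sound parts.

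- *Appendix H looks like a general template.* It lists uric acid, cholesterol, triglycerides, HbA1c and CRP, none of which is in Protocol Table 11-1, and it has orthostatic rows. Clearance is not in Table 11-1 either, and SAP 10.4.2 does not derive it. So the clearance row may never be produced, and a forecast of widespread renal impairment is not supported. Creatinine and weight are collected, however, so both rows can be run, and the SAP exempts neither.
- *The percent-change creatinine criteria (30% and 100%) are already in Table 13-9.* True; a baseline-referenced renal criterion exists without the clearance row.
- *The 24-week columns are much less affected.* True. The comparison of L200/I with Placebo within the parent studies is like for like. A reader might infer that nearly every subject is flagged in every column, but Steps 1 to 3 do not support that.
- *Baseline is defined per Study Period, and the weight row does not say which applies.* True. Measuring from the Study 110 baseline shortens the interval to 96 weeks, which still leaves a break-even of only 2.7% a year.
- *Growth faltering is not lost.* A reader might infer that a child falling away from the growth curve is missed. In fact weight, height and BMI z-scores are modelled at each visit, and SAP 10.4.4 lists all vital-sign values. What is absent is a z-score count in a safety table. Heart rate and blood pressure also have their own counts in Table 10-7, and blood pressure has percentiles adjusted for sex, age and height.
- *The Protocol 8.2.3 sentence concerns nutritional status, not safety limits.* This is so, but its reason, that children grow, applies equally to an unadjusted weight-gain count.
- *The tables are descriptive.* True; no test depends on them.

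**Conclusion.** The weight point holds. That a gain of 2.7% a year passes the criterion by week 96, and 2.1% by week 120, follows from the documents and arithmetic alone. That most children will pass it rests on assumed growth: 78% to 97% by week 96 for mean gains of 5% to 10% a year, against 2% to 39% within 24 weeks. The row is therefore uninformative in the long-period columns, would dominate the combined vital-sign count, and would favour the appearance of an excess under L/I Overall relative to Placebo.

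The clearance point holds as a specification fault: the age limit given to the absolute creatinine cut was not carried to the row below. Its effect is conditional on the assumed formula and creatinine values. It reaches roughly 18 to 25 kg children, with girls affected first and up to 28 kg at 0.6 mg/dL.

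It would go too far to say that the primary safety analysis counts normal children as abnormal. The SAP calls these threshold criteria, the liver criteria are multiples of the upper limit of normal and are not affected in this way, and safety is summarised without testing. This is a correction that should be made to the table specification; it does not threaten the trial's conclusions.

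**What to change.** - In Table 13-11, replace the criterion for a gain of 5% or more with a change in weight-for-age z-score, with a cut stated in advance. Alternatively, keep the row but exclude it from the SAP 10.4.4 count of subjects meeting one or more criteria. Keep the 5% loss criterion in either case.
- State which baseline the weight row uses in each column, and add a footnote giving the different observation times of Placebo and L/I Overall.
- In Table 13-9, restrict the clearance row to adults or drop it, and rely on the percent-change creatinine criteria already there.
- Add one sentence to Appendix H saying which rows apply to this study.

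The cost is an edit to the SAP tables and their shells. The z-score is already derived, and no new data, visits or sample-size work are needed.
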